4 STUDY DESIGN

4.1 Overall design

This is a randomized, open-label Phase 3 extension study to evaluate the long-term safety, tolerability, and efficacy of rozanolixizumab in study participants with generalized MG. A study schema is provided in [Figure 1-1](#) and a Schedule of Activities is provided in [Table 1-1](#).

Study participants will enter MG0004 from lead-in studies MG0003 or MGC003. Study participants in MG0003 or MGC003 who complete the Observation Period or who require rescue medication during the Observation Period will be invited to be rerandomized in MG0004 (except for study participants who opt to receive IVIg or PEX as rescue medication). Study participants who receive IVIg or PEX as rescue therapy during the Observation Period of MG0003 or MGC003 will not be eligible to enroll in MG0004. Study participants who discontinue study medication in MG0003 or MGC003 for any reason other than requiring rescue medication will not be eligible for MG0004.

For any study participant who enrolls in MG0004, the final visit in MG0003 (Visit 14) or MGC003 will serve as the first visit in MG0004 (Visit 1). All activities should be completed at Visit 1 (± 1 week). For criteria pertaining to laboratory measures, the last available value from MG0003 or MGC003 will be used for evaluation of study participant eligibility, as long as the

measurement was taken within the last 4 weeks (not older than 32 days) prior to MG0004 Screening. Up to approximately 276 study participants will be enrolled into the lead-in study MG0003 and MGC003. All eligible study participants from MG0003 or MGC003 will be invited to participate in MG0004.

In MG0004, study participants will be randomized in a 1:1 ratio to receive 1 of 2 doses of rozanolixizumab (equivalent to approximately [REDACTED], respectively). Specifically, the following dose arms will be used in the study:

Dose arm 1: equivalent to approximately [REDACTED] rozanolixizumab

- Bodyweight <50kg: dose to be administered [REDACTED]
- Bodyweight \geq 50kg and <70kg: dose to be administered [REDACTED]
- Bodyweight \geq 70kg and <100kg: dose to be administered [REDACTED]
- Bodyweight \geq 100kg: dose to be administered [REDACTED]

Dose arm 2: equivalent to approximately [REDACTED] rozanolixizumab

- Bodyweight <50kg: dose to be administered [REDACTED]
- Bodyweight \geq 50kg and <70kg: dose to be administered [REDACTED]
- Bodyweight \geq 70kg and <100kg: dose to be administered [REDACTED]
- Bodyweight \geq 100kg: dose to be administered [REDACTED]

If one of the doses described above is determined to be futile and is discontinued after the interim analysis in MG0003 or MGC003, then that dose arm will be dropped from MG0004 as well, and study participants in the affected dose arm will be transferred to the continuing dose arm. If both dose arms are used in MG0004, study participants will be allowed to switch dose arms for tolerability and efficacy reasons at the discretion of the Investigator (see Section 6.6).

In MG0004, rozanolixizumab will be administered SC on a [REDACTED] basis over a 52-week Treatment Period. Weekly visits will be either on-site or at home, as described in the Schedule of Activities (Section 1.3). During the first 4 weeks, the weekly visits will be on-site. From Weeks 5 to 8, on-site visits and at home visits will occur on an alternating basis. From Weeks 9 to 48, study participants will have 1 site visit every 4 weeks, such that 1 site visit will be followed by 3 home visits, unless the study participant chooses to complete the scheduled at-home assessments at the site. Weeks 49 to 51 will then involve 1 site visit followed by 2 home visits. At the end of the 52-week Treatment Period in MG0004, study participants will participate in an 8-week Observation Period.

In exceptional circumstances (eg, pandemic, hurricanes, etc) where study-specific investigations may not be conducted according to study protocol, contingency measures will be in place (see Section 8).

This OLE study will be replaced by MG0007, an OLE study with [REDACTED] based on MG worsening. Upon study site approval of MG0007, as well as fulfilment of regulatory requirements, study participants will have the opportunity to rollover directly into MG0007 and will no longer have the opportunity to rollover to MG0004. In the event a study participant has

already started MG0004, a minimum treatment duration of 6 visits must be completed (if IMP treatment is withheld for low IgG, study participants missed dose(s) can be counted as part of the total 6 visits for completion of MG0004 and meet eligibility requirements for MG0007) and then the participant will discontinue MG0004 and have the opportunity to enter into MG0007. For study participants entering MG0007 from the treatment period of MG0004, he/she must complete the PEOT Visit in MG0004 which will serve both as the Screening Visit for MG0007 and as the EOS for MG0004. If a study participant completes the Treatment Period and is in the Observation Period of MG0004, he/she will then complete the EOS visit to serve as the Screening Visit for MG0007. Once the site is active for MG0007, no further participants will enroll in MG0004 and the study will be closed at the site once all eligible study participants have rolled over into MG0007.

An IDMC will be formed to monitor the ongoing safety of the study. The IDMC will review implications of individual and cumulative cases to continuance of the study in an ongoing fashion.

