8.3.1 Time period and frequency for collecting AE and SAE information

All SAEs will be collected from the signing of the ICF until EOS Visit at the time points specified in the Schedule of Activities (Section 1.3).

All AEs will be collected from the signing of the ICF until EOS Visit at the time points specified in the Schedule of Activities (Section 1.3).

All SAEs will be recorded and reported to the Sponsor or designee within 24 hours, as indicated in Appendix 3 (Section 10.3). The Investigator will submit any updated SAE data to the Sponsor within 24 hours of it being available.

The Investigator is specifically requested to collect and report to UCB (or its representative) any SAEs (even if the Investigator is certain that they are in no way associated with the study medication), up until the End of Study Visit for each participant, and to also inform participants of the need to inform the Investigator of any SAE within this period. Serious AEs that the Investigator thinks may be associated with the study medication must be reported to UCB regardless of the time between the event and the end of the study.

The method of recording, evaluating, and assessing causality of AE and SAE and the procedures for completing and transmitting SAE reports are provided in Appendix 3 (Section 10.3).

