2.2 Study endpoints

2.2.1 Safety endpoints

2.2.1.1 Primary safety endpoints

- Occurrence of treatment-emergent adverse events (TEAEs)
- Occurrence of TEAEs leading to permanent withdrawal of study medication

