2.4 Determination of sample size

No formal sample size calculation can be performed. Up to approximately 240 study participants will be enrolled into the lead-in study MG0003. All eligible study participants from MG0003 will be invited to participate in MG0004 until study site approval of MG0007 as well as fulfilment of regulatory requirements.

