3.9 Changes to protocol-defined analyses

- The following two exploratory endpoints will not be analyzed as they have been removed from the MG program as a whole and have been included in the protocol in error:
 - Change from Baseline in the MG Symptoms PRO multicomponent total score, at each scheduled assessment during Treatment and Observation Periods,
 - Change from Baseline in the enhanced MG Symptoms PRO total score, at each scheduled assessment during Treatment and Observation Periods.
- The increase or reduction in use of concomitant medications will be analyzed in the SAP, so objective is changed to “To assess the dose change in use of concomitant medications in study participants receiving rozanolixizumab” in the SAP.

- The dose change in use of concomitant medications in study participants receiving rozanolixizumab will be analyzed using number and percentage of participants with dose change of concomitant medications and change from Baseline in ADD in the study. There is no concentration data of concomitant medications in the study to generate area under the curve (AUC), so it is not included in the SAP.
- No study participants from MGC003 will rollover into MG0004. Thus, the maximum sample size of this study should be 240, not 276.

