4 STATISTICAL/ANALYTICAL ISSUES

4.1 Adjustments for covariates

Statistical testing is not planned for this study, hence adjustment for covariates will not be required.

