5 STUDY POPULATION CHARACTERISTICS

5.1 Subject disposition

The following outputs will be created.

Summaries:

- **Reasons for screen failures** (as collected on the Study Termination Screen Failure CRF page) will be summarized using the ES for overall. Additionally, the reasons for screen failures will be summarized by pre-, during and post- the COVID-19 pandemic based on the screen failure date relative to the pandemic cut-off date.
- **Disposition of study participants screened** will be summarized using the ES for overall, by region and by site. In this summary, the site number, principal investigator name, first participant in date and last participant out date, will be captured by randomized treatment and by each analysis set (RS and SS).
- **Disposition of analysis sets** will be summarized by treatment groups and analysis sets (RS and SS) using the RS.

- **Disposition and discontinuation reasons** using the RS and SS will contain the number and percentage of study participants by treatment group and RLZ total and also by pre-, during and post- the COVID-19 pandemic who:
 - Started Study,
 - Completed Study,
 - Discontinued Study with
 - Primary Reason for discontinuation, including transitioned to study MG0007 (primary reason for premature study termination as collected in the Study Termination Enrolled CRF).

Note: The summary by pre-, during and post- the COVID-19 pandemic will be based on the start, completed and discontinuation date relative to the pandemic cut-off date will be presented in the same table. The discontinuation reason in each period will also be summarized. Discontinuation due to COVID-19 pandemic will be listed as sub-category under “Other” reason.

- **Discontinuation due to AEs** using the RS and SS will summarize the total number of study participants who discontinued the study due to AEs by treatment group and the categories: AE, serious fatal, AE non-fatal and other (AE non-serious fatal).
- **Count of participant by visit** using SS will summarize the number of participants at each visit by treatment group.
- **Impact of COVID-19 pandemic** using the RS will summarize number and percentage of participants in each impact category by visit.

Listings of study participant disposition, study discontinuation and study participants who did not meet study eligibility criteria will be provided.

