8.2 Adverse events

8.2.1 Data considerations

Adverse events will be recorded from the time of informed consent until study completion. All AEs will be coded as described in [Section 3.8](#).

In addition, AEs will be classified according to the Common Terminology Criteria for Adverse Events (CTCAE) Version 5 or later for severity. For any AEs where it is not possible to provide a CTCAE grading, the events will be assessed using a standard intensity classification (mild, moderate and severe). For the purpose of reporting severe AEs, all CTCAE severity classifications will be mapped to a standard intensity classification as described below:

- Grade 1 - Mild

- Grade 2 - Moderate
- Grade 3, 4, 5 - Severe

These will be tabulated together with the AEs that were not classified according to CTCAE criteria (i.e., all Grade 1 AEs as per CTCAE criteria will be included in the ‘mild’ category together with those AEs classified as mild as per the standard intensity classification). In the case a mapped standard intensity classification per above rule is different from the standard intensity classification on CRF, the worst case will be used as the standard intensity classification (i.e. an AE with Grade 1 and moderate as intensity classification will be classified into moderate).

A TEAE is defined as an AE starting on or after the time of first administration of IMP in MG0004 or any unresolved event already present before the first administration of IMP in MG0004 that worsens in intensity following exposure to IMP in MG0004, up to and including 8 weeks (56 days) after the end of the Treatment Period or 8 weeks after the last of IMP in study participants who discontinue the study or IMP.

A persistent AE is defined as an unresolved AE that extends continuously from MG0003 to MG0004 and does not worsen in intensity following exposure to IMP in MG0004. Persistent AEs will be recorded in MG0004 database and as other non-TEAEs will be listed only.

Where dates are missing or partially missing, AEs will be assumed to be treatment-emergent unless evidence exists that does not allow the AE to be treatment-emergent. Handling of missing dates for classification of AEs as TEAEs is described in [Section 4.2.2](#).

The following rules will be used to assign a TEAE to a study period:

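### Participants who leave the Treatment Period for MG0007 exit MG0004 AE collection about 7 weeks before the TEAE window closes, and crude percentages pool them with 60-week completers without any person-time

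*Protocol*

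**What the plan says.** - **Exit route.** Once a site opens MG0007, a participant already in MG0004 completes at least 6 visits, then discontinues MG0004 and may enter MG0007 (Protocol 4.1). For those leaving the Treatment Period, "he/she must complete the PEOT Visit in MG0004 which will serve both as the Screening Visit for MG0007 and as the EOS for MG0004". Those already in the Observation Period complete the EOS visit itself. SAP 5.1 tabulates "Primary Reason for discontinuation, including transitioned to study MG0007".
- **AE collection.** Protocol 8.3.1: "All AEs will be collected from the signing of the ICF until EOS Visit at the time points specified". SAEs that the investigator thinks may be drug-associated remain reportable without time limit.
- **TEAE window.** SAP 8.2.1 extends it 56 days beyond the Treatment Period and, for early leavers, adds "or 8 weeks after the last of IMP in study participants who discontinue the study or IMP". Protocol 8.3.8 also uses 8 weeks after the final dose.
- **Display.** SAP 8.2.1 and 8.2.2 show TEAEs on the Safety Set as participants, percentage and event count, by most recent dose. No person-time is planned. Exposure (SAP 8.1) is summarized by first dose.
- **Inference.** None: "Statistical testing is not planned for this study" (SAP 4.1) and "No formal sample size calculation can be performed" (SAP 2.4).

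**The concern.** The first primary endpoint, occurrence of TEAEs, has a window that closes 8 weeks after the last dose. For Treatment Period transfers, MG0004 stops asking about AEs roughly one week after that dose. No passage in either document ends the window early for them or brings later events back. The sponsor's own rationale (Protocol 4.2) is that 8 weeks is the time antibodies are expected to need to return to Baseline, so the uncovered weeks are relevant to safety.

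Transfer is a planned exit, possible after a short course. A participant seen for six weeks and one seen for sixty then carry the same weight in a percentage presented as long-term safety. At stake is how far that percentage understates incidence, for reasons tied to the MG0007 opening dates rather than to the drug.

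**Working it through.** **Inputs**
- TEAE window after last IMP: 56 days (SAP 8.2.1).
- Treatment Period 52 weeks, Observation Period 8 weeks (SAP 3.2.2).
- Visits weekly (Protocol 4.1), each ±2 days (Schedule of Activities, footnote b).
- Dosing interval: redacted. Weekly is assumed; the top infusion category of 49-52 in SAP 8.1 is consistent with it.
- No IMP at PEOT for those who stop (footnote m).
- Minimum before transfer: 6 visits (Protocol 4.1).
- Maximum N: "the maximum sample size of this study should be 240, not 276" (SAP 3.9).
- Event rates, transfer shares and transfer times: not in the documents; assumed below.

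**1. The plan's own figures.** 8 × 7 = 56 days and 52 + 8 = 60 weeks, as stated. A completer has the last dose on Day 1 + 51 × 7 = 358 and EOS on Day 1 + 59 × 7 = 414. 414 − 358 = 56, so the whole window is observed.

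**2. Window for a Treatment Period transfer.** With PEOT 7 days after the last dose, 56 − 7 = 49 days are uncovered (87.5%). With the two visits at opposite ends of their ±2-day windows the gap is 3 to 11 days, leaving 53 to 45 uncovered. With one dose missed before PEOT the gap is 14 days, leaving 42 (75%).

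**3. Follow-up.** After 6 weekly dosing visits the last dose is on Day 1 + 5 × 7 = 36 and PEOT on Day 43. 414 / 43 = 9.6.

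**4. Lost window or shorter treatment?** Take expected incidence = 1 − exp(−rate × days / 365.25), with an assumed 0.5 events per participant-year:

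| Follow-up | Days | Incidence |
|---|---|---|
| Minimum-course transfer, as observed | 43 | 5.7% |
| Same, full 56 days after last dose | 36 + 56 = 92 | 11.8% |
| Completer | 414 | 43.3% |

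The lost window accounts for 11.8 − 5.7 = 6.1 points. Shorter treatment accounts for 43.3 − 11.8 = 31.5.

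**5. A less extreme mix.** Assume half transfer after 24 doses, with 20 events per 100 participant-years. Days elapsed from first dose are 23 × 7 + 7 = 168 observed, 23 × 7 + 56 = 217 with the full window, and 413 for a completer.
- As planned: 14.5%.
- Full window covered: 15.7%.
- Everyone completes: 20.2%.

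The window costs 1.2 points and shorter treatment 4.5. With transfers still after 24 doses, transfer shares of 25-75% and rates of 5-100 per 100 participant-years, the window costs 0.2 to 5.9 points. The total shortfall runs from 5.5 − 4.7 = 0.8 to 67.7 − 44.6 = 23.1 points.

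**6. Uncovered person-time.** 240 × share × 49 / 365.25 gives 8.1, 16.1 and 24.2 participant-years for shares of 25, 50 and 75%. At 20 per 100 participant-years that is 1.6, 3.2 and 4.8 events.

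**7. Which tables are exposed.** SAP 8.2.1 ends the Treatment Period for TEAEs 7 days after the last dose, about where PEOT falls. The Treatment Period TEAE table in SAP 8.2.2 therefore compares roughly like windows. The only other outputs limited in this way are the headache and gastrointestinal AEOF summaries by intensity and the headache graphs (SAP 8.2.3).

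**The case against.** The case against has real force.

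- **Both primary endpoints.** A reader might infer that the lost weeks bias both. They do not: IMP has already stopped by PEOT, so later events cannot materially cause its permanent withdrawal. That endpoint is touched only by shorter time on treatment.
- **All transfers.** A reader might infer that everyone moving to MG0007 is affected. Observation Period transfers complete the EOS visit itself.
- **The large contrast.** A reader might attribute 5.7% against 43.3% to the lost window. Step 4 shows that it is mostly treatment duration, at the most extreme transfer time.
- **Events in neither study.** A reader might infer that events between PEOT and the first MG0007 dose are treatment-emergent nowhere. The MG0007 protocol is not available, so its collection start, first-dose timing and TEAE definition cannot be checked. The documents support only that MG0004 does not collect these events.
- **Uninterpretable percentages.** Too strong. The Treatment Period table, exposure summaries, counts by visit and discontinuation reasons are planned, and suspected drug-associated SAEs stay reportable.
- **Arm comparison.** Allocation is 1:1, and nothing documented links MG0007 opening to dose.

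What the objection leaves standing is the absence of a TEAE end date for Treatment Period transfers and of any person-time. Readers cannot derive rates themselves, because exposure is grouped by first dose and TEAEs by most recent dose. SAP 3.1 has an observed-data denominator for safety endpoints, but does not say how it applies to AE occurrence, so it does not clearly remove transfers.

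**Conclusion.** The point holds for Treatment Period transfers. About 49 of 56 post-dose days (45 to 53 across visit windows) fall outside MG0004 AE collection, which affects occurrence of TEAEs. This rests on weekly dosing and no dose withheld before PEOT.

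Unequal follow-up is the bigger matter: about 43 against 414 days within one denominator. Crude percentages understate long-term incidence, by 0.8 to 23.1 points across the assumed mixes, most of it from shorter treatment. The actual size depends on how many participants transferred and when, neither of which is stated.

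The Treatment Period table largely removes the window gap for any TEAE. It does not do so for the serious, severe, related and AESM tables or most AEOF tables, and it does not adjust for duration. The study is descriptive, so no test is compromised. This is an inexpensive improvement worth making.

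**What to change.** 1. **SAP 8.2.2 and 8.2.3.** Add to the TEAE overview and to the main TEAE, serious, AESM and AEOF tables the participant-years of observed follow-up, plus participants with event and events per 100 participant-years. Assign person-time by most recent dose, to match the TEAE columns, and end it at the participant's last MG0004 AE collection date.
2. **SAP 8.2.1.** State that for Treatment Period transfers the observed TEAE window ends at the PEOT/EOS visit. Use the Treatment Period TEAE table as the main comparison of crude percentages.
3. **Reconcile three passages for transfers.** Protocol 4.1 makes PEOT both MG0007 Screening and MG0004 EOS. SAP 2.3 words these as alternatives. Protocol 7.2 sends those who stop medication to PEOT and then the Observation Period, without excepting transfers. Item 2 should follow whatever this settles.

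Bringing in MG0007 AEs is optional and depends on collection rules not in these documents.

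The cost is extra table columns and a person-time derivation split by dose. The rates assume a roughly constant hazard, so they belong beside the crude percentages, not in place of them.

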4.2 Scientific rationale for study design

The lead-in studies, MG0003 and MGC003, will evaluate the efficacy, safety, and tolerability of rozanolixizumab compared with placebo in study participants with generalized MG who are treated with study medication over a [REDACTED] at [REDACTED]. Study participants in the lead-in studies will have generalized MG, as evidenced by the presence of anti-AChR or anti-MuSK antibodies. Additionally, study participants in the lead-in studies will have moderate to severe symptoms of MG and should be under consideration for IVIg or PEX therapy, indicating that they are in need of additional therapeutic intervention.

Study participants in MG0003 or MGC003 will be randomized to receive either placebo or 1 of 2 doses of rozanolixizumab. Study participants in MG0003 or MGC003 who require rescue medication (other than IVIg or PEX) during the Observation Period will be invited to be rerandomized in MG0004: this will offer all study participants, even those previously treated with placebo, a chance to be treated with rozanolixizumab. Rerandomization in MG0004 is applied to account for the limited efficacy information on the [REDACTED] dose. Due to the open-label design of MG0004, study participants are allowed to switch dose at the Investigator's discretion during the course of the study (dose modification recommendations for safety are provided in Section 6.6). Study participants developing TEAEs could be switched to a dose equivalent to [REDACTED] and study participants experiencing symptom worsening can be switched to a dose equivalent to [REDACTED].

MG0004 will then evaluate the long-term safety, tolerability, and efficacy of rozanolixizumab over a 52-week Treatment Period. An open-label study with a treatment duration of 52 weeks is considered sufficient to adequately assess long-term safety with rozanolixizumab for the proposed indication. The dose regimen for rozanolixizumab in MG0004 will be the same one that is used in MG0003 and MGC003 (equivalent to approximately [REDACTED]), although the dose may be modified based on interim analysis in MG0003 (Section 4.3). In MG0004, study participants will be rerandomized to 1 of 2 doses of rozanolixizumab, and will be allowed to switch between dose arms at the discretion of the Investigator. MG0004 will therefore allow study participants to switch their dose of study medication on an individual basis. MG0004 also offers study participants the chance to benefit from long-term treatment. MG0004

will conclude with an 8-week Observation Period, which is the anticipated duration of time required for antibodies to return to Baseline levels after rozanolixizumab treatment.

